#### **6.1.1.2.7. Time to discontinuation from IP due to Gastrointestinal Disorders AEs**

Exploratory summaries on the time to discontinuation from IP (regardless of study discontinuation or continuation) due to Gastrointestinal Disorders AEs (defined as based on System Organ Class) will be produced with a Cumulative Incidence Plot as described in Section 5.2.4. Participants who discontinue will be censored at the associated discontinuation date. There will be a separate line for each treatment group.

#### **6.1.1.2.8. Subset reporting interval**

The number and percentage of TEAEs of interest defined based on the subset reporting interval (described in Section 3.5.1.2) will be summarized by treatment group and overall. A separate table representing the number and percentage by severity (mild, moderate or severe) will also be produced. These tables will be produced separately for each TEAE of interest.

#### **6.1.1.2.9. Hypoglycemic Adverse Events**

The hypoglycemic AEs will be listed in a separate table and summarized categorically by treatment and overall as per Section 5.2.2.

CCI

## **6.2. Secondary Endpoint(s)**

### **6.2.1. Change from Baseline in FPG at Weeks 2, 4, 6, 8, 10 and 12 in participants with T2DM**

#### **6.2.1.1. Main Analysis**

In all cases the Estimand Set 1A as specified in Section 4 will be utilized, which notably will only include T2DM participants.

Absolute values and changes from baseline in FPG will be summarized descriptively by treatment group and time point as described in Section 5.2.1. Tables will present all data from the screening (visit 1, absolute tables only), beginning of the placebo run-in (visit 2, absolute tables only), baseline and post-baseline time points (including follow-up, which will be restricted to participants who completed 12 weeks of treatment and did not initiate glycemic rescue medication). Box and whisker plots of absolute values and changes from baseline will also be separately produced.

The analysis will be an MMRM (as described in Section 5.2.3) applied to the change from baseline at Weeks 2, 4, 6, 8, 10 and 12 that will be used to estimate the treatment effect related to the secondary Estimand 1A (as described in Section 2.1.2).

The following results from the above primary analysis will be plotted:

- Profile plots of the LSMeans (including 90% confidence intervals) over time, with a separate line for each treatment group
- Profile plots of the LSMean differences to Placebo (including 90% confidence intervals) over time, with a separate line for each treatment group of PF-06882961

Standard SAS output will be provided to support the main statistical summary table for the secondary analysis model but will not be included in the CSR.

#### Statistical Model Diagnostics

The presence of outliers will be investigated for this analysis. An outlier will be defined as any response data value with a studentized (conditional) residual greater than 3, or less than -3. A listing will be presented of any participants meeting these criteria and will be included with standard SAS outputs. The assumptions of normality will be verified graphically using residual plots. For each fitted model, a set of conditional studentized residual plots will be produced, including residual plot, histogram of normality, QQ plot and summary of fit statistics. The residual plots will not be included in the clinical study report.

If there are outliers or major deviations from normality, then the effect of these on the conclusions may be investigated through alternative transformations and/or analyses excluding outliers. Justification for any alternative to the planned analysis will be given in the report of the study.

### **6.2.2. Change from Baseline in HbA1c at Weeks 2, 4, 6, 8, 10 and 12 in participants with T2DM**

#### **6.2.2.1. Main Analysis**

In all cases the Estimand Set 1A as specified in Section 4 will be utilized, which notably will only include T2DM participants.

The summaries and analysis for HbA1c will be similar to that for FPG, as specified in Section 6.2.1.1 to estimate the treatment effect related to the secondary Estimand 2A (as described in Section 2.1.2).

### **6.2.3. Change from Baseline for Body Weight at Weeks 2, 4, 6, 8, 10 and 12 in participants with T2DM**

#### **6.2.3.1. Main Analysis**

In all cases the Estimand Set 1A as specified in Section 4 will be utilized, which notably will only include T2DM participants.

The summaries and analysis for body weight will be similar to that for FPG, as specified in Section 6.2.1.1 to estimate the treatment effect related to the secondary Estimand 3A (as described in Section 2.1.2)

### **6.2.3.2. Supplementary Analyses**

The percent change from baseline in body weight at Weeks 2, 4, 6, 8, 10 and 12 will additionally be summarized and analyzed as per Section 6.2.1.1.

For the MMRM model, all body weight values (including baseline) will be  $\log_e$ -transformed prior to analysis (i.e. the outcome in the model will be the difference of the  $\log_e$  absolute value at the time point of interest minus the  $\log_e$  baseline). All LSMeans and LSMean differences (including confidence intervals) will be back-transformed to give geometric LSMeans and ratios of geometric LSMeans.

The percent change will then be calculated as follows:

$$\text{Percent change} = 100 * (\text{back-transformed LSMean} - 1)$$

### **6.2.4. Change from baseline in body weight at Weeks 2, 4, 6 8, 10 and 12 in non-diabetic participants with obesity**

#### **6.2.4.1. Main Analysis**

In all cases the Estimand Set 1B as specified in Section 4 will be utilized, which notably will only include non-diabetic participants with obesity.

The summaries and analysis for body weight will be similar to that for FPG, as specified in Section 6.2.1.1 to estimate the treatment effect related to the secondary Estimand 3B (as described in Section 2.1.2).

#### **6.2.4.2. Supplementary Analysis**

Similar supplementary analyses of the percent change from baseline in body weight as described in Section 6.2.3.2 will be performed using the Estimand Set 1B.

### **6.3. Other Endpoint(s)**

#### **6.3.1. Pharmacokinetic Endpoints**

PF-06882961 concentrations will be characterized by  $C_{\text{trough}}$  and will be summarized by treatment and by time point using the following descriptive statistics: number of subjects contributing at each time point, arithmetic mean, median, minimum, maximum, Q1, Q3, standard deviation, geometric mean, and geometric CV (%).

Median  $C_{\text{trough}}$  versus time point will be plotted by dose including error bars representing the inter-quartile range (i.e. Q1 to Q3).

$C_{\text{trough}}$  values from PK samples that were collected after discontinuation of investigational product will be listed but excluded from summarization.

PF-06882961 concentrations assessed during random collection (i.e. ~2-6 hours post-dose and unplanned measurements) will only be listed (and not summarized); these data are noted for use in supplemental population-PK analyses as required.

In addition, as permitted by data and determined by the sponsor, PK-PD relationship between plasma concentrations of PF-06882961 and effect on primary, secondary and tertiary endpoints may be characterized using a population PK-PD approach. The objective of such an analysis, if conducted, would aim to explore potential demographic determinants (eg, age, gender, and weight) influencing the observed PK or PD variability in response to PF-06882961. The population PK-PD analysis, if conducted, will be reported separately from the main CSR.

### **6.3.2. Change from Baseline in FPG at Weeks 2, 4, 6, 8, 10 and 12 in non-diabetic participants with obesity**

In all cases the Estimand Set 1B as specified in Section 4 will be utilized, which notably will only include non-diabetic participants with obesity.

The summaries and analysis will be similar to that for FPG, as specified in Section 6.2.1.1 to estimate the treatment effect related to the Estimand 1B (as described in Section 2.1.3).

### **6.3.3. Change from Baseline in HbA1c at Weeks 2, 4, 6, 8, 10 and 12 in non-diabetic patients with obesity**

In all cases the Estimand Set 1B as specified in Section 4 will be utilized, which notably will only include non-diabetic participants with obesity.

The summaries and analysis for HbA1c will be similar to that for FPG, as specified in Section 6.2.1.1 to estimate the treatment effect related to the Estimand 2B (as described in Section 2.1.3).

## **6.4. Subset Analyses**

N/A

## **6.5. Baseline and Other Summaries and Analyses**

Where relevant, data will be reported in accordance with the sponsor reporting standards.

### **6.5.1. Baseline Summaries**

A baseline table (or separate tables, as required) summarizing the following will be produced by treatment group and overall (T2DM and non-diabetic obesity, summarized separately): age; gender; race; ethnicity; height; weight; body mass index; duration of T2DM (for T2DM participants only); HbA1c; fasting plasma glucose; systolic blood pressure; diastolic blood pressure; pulse rate; eGFR and duration of metformin & total daily dose (for T2DM participants only).

### **6.5.2. Study Conduct and Participant Disposition**

Participant evaluation groups will show participant disposition for each phase of the study (double-blind treatment and follow-up) and will additionally show which participants were

analyzed for efficacy (Estimand Set 1A and 1B) as well as for safety. Frequency counts and percentages will be supplied for participant discontinuation(s) by treatment group and overall.

A summary table of important protocol deviations (IPDs) will be produced by treatment group and overall. An additional summary table restricted to coronavirus disease 2019 (COVID-19) related IPDs only will also be produced if such deviations occur. Listings related to both tables will be produced regardless of whether such deviations occur or not.

#### **6.5.3. Banked Biospecimens**

Banked biospecimens will be collected and retained for future analyses, but will not be analyzed specifically for this study and will not be included in the CSR.

#### **6.5.4. Concomitant Medications and Nondrug Treatments**

All prior and concomitant medication(s) as well as non-drug treatment(s) will be reported according to current sponsor reporting standards.

A separate table listing the use of rescue medication will be produced according to current sponsor reporting standards. The use of rescue medication (grouped by class of medication) will be summarized descriptively by treatment group and overall as described in Section 5.2.2. The classes will be defined based on medications used in the study.

#### **6.5.5. Treatment Compliance**

A summary table of treatment compliance (by treatment group and overall) will be produced according to current sponsor reporting standards.

#### **6.5.6. Discontinuations**

Participant discontinuations, temporary discontinuations or dose reductions due to adverse events will be detailed and summarized by treatment group and overall.

Data will be reported in accordance with the sponsor reporting standards, where an additional table summarizing participant discontinuations due to adverse events for each system organ class and preferred term will be produced by treatment group and overall also.

Exploratory summaries on the time to discontinuation from the study and time to discontinuation from IP (regardless of study discontinuation or continuation) will be produced separately using Cumulative Incidence Plots as described in Section 5.2.4. For both, participants who discontinue from the study/IP will be censored at the associated discontinuation date.

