## 5.2. General Methods

The analyses related to the primary, secondary and exploratory endpoints will be based on the appropriate population for analysis (see Section 4).

Unless otherwise stated, all summaries and plots will be presented by treatment group. The following treatment group labels (or similar) will be used:

Arm	Strata	Treatment group label
5	T2DM	Placebo (T2DM)
5	Non-diabetic obesity	Placebo (non-diabetic obesity)
3	T2DM	PF-06882961 80 mg BID low, slow (T2DM)
4	T2DM	PF-06882961 80 mg BID high, slow (T2DM)
1	T2DM	PF-06882961 120 mg BID low, fast (T2DM)
2	T2DM	PF-06882961 120 mg BID high, fast (T2DM)
6	T2DM	PF-06882961 200mg BID (T2DM)
7	Non-diabetic obesity	PF-06882961 200mg BID (non-diabetic obesity)

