#### **5.2.4. Cumulative Incidence Plots**

Cumulative Incidence Plots will be produced based on the time to the event of interest (starting from the time of start of dosing on Day 1) for each treatment group separately and will be plotted on the same graph. This will be based on plotting the cumulative incidence function (with no competing risks), which will be presented as a % on the y-axis. No statistical testing for differences between treatment groups will be considered.

Details of censoring are included in Sections 6.5.6, 6.1.1.2.6 and 6.1.1.2.7 and example SAS code is provided in Appendix 2.

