##### **6.1.1.2.6. Time to first occurrence/recurrence of adverse events of interest**

Time to the first occurrence of TEAEs of interest will be produced using Cumulative Incidence Plots as described in Section 5.2.4. Participants who discontinue from the study, discontinue from IP or initiate glycemic rescue medication prior to the start of the TEAE of interest will be censored at the discontinuation/initiation date.

A separate plot for each TEAE will be produced separately.

The above will also be produced separately for the time to the first recurrence of the TEAEs of interest. There will be a separate line for each treatment group.

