### Example SAS code for Cumulative Incidence Plots:

```
proc lifetest data = dataset method=km plots=cif(test) outcif=cifatrisk intervals=0 to 20 by 2;
  strata treatment;
  time day*censor(1)/eventcode=0;
run;
```

NOTE: the censor variable has a value = 1 when the related time is censored and has a value = 0 when the event of interest occurs. There should be no other values available for this censored variable in this dataset (including missing values). If required, missing observations should be removed prior to analysis.

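### SAP 6.5.6 censors participants at discontinuation in plots whose event is discontinuation, so as written both plots have no events and stay at 0%

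*SAP*

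**What the plan says.** SAP 6.5.6 (Discontinuations) announces "Exploratory summaries on the time to discontinuation from the study and time to discontinuation from IP", the latter regardless of whether the participant stays in the study. Each is to be shown as a cumulative incidence plot by the method of SAP 5.2.4. The section closes with the censoring rule: "For both, participants who discontinue from the study/IP will be censored at the associated discontinuation date".

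SAP 5.2.4 (Cumulative Incidence Plots) bases these plots on time from first dosing to the event of interest, with no competing risks. Curves are drawn "for each treatment group separately and will be plotted on the same graph". It sets no censoring rule of its own: "Details of censoring are included in Sections 6.5.6, 6.1.1.2.6 and 6.1.1.2.7".

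SAP Appendix 2 fixes the coding for the example SAS code. The censor variable has "value = 1 when the related time is censored and has a value = 0 when the event of interest occurs", and no other value is allowed.

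**The concern.** In a time-to-event display, a participant who reaches the event counts as an event at that time. A participant who leaves observation without reaching it is censored. SAP 6.5.6 gives both roles to the same people on the same date: discontinuation is what the plot measures, and it is also the reason for censoring. The coding in Appendix 2 does not allow both.

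The timing of discontinuation is at stake. The trial compares starting doses, titration step lengths and target doses for tolerability, so when participants stop relative to the titration steps is of interest. These are the only planned curves of all-cause discontinuation. SAP 6.1.1.2.7 covers only IP discontinuation due to gastrointestinal AEs. Programmed as written, the two plots would show nothing. A programmer who notices has to depart from the SAP text to produce a usable figure.

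**Working it through.** **Inputs**

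- Event: discontinuation from the study (plot 1) or from IP (plot 2). SAP 6.5.6.
- Censoring rule: discontinuers censored at their own discontinuation date, in both plots. SAP 6.5.6.
- Codes: 1 = censored, 0 = event, nothing else. SAP Appendix 2.
- Estimator: cumulative incidence without competing risks, which equals 1 − Kaplan-Meier. SAP 5.2.4.
- Treatment groups: 8 labels. SAP 5.2.
- Planned size: about 140 randomized, 25% drop-out, about 105 completing. Protocol 9.2 and SAP 2.2.
- Earlier 28-day study: 6 of 98 discontinued. Protocol 2.2.2.1.

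**The plan's own figure.** 140 × (1 − 0.25) = 105 completers, as stated. Planned drop-outs are 140 − 105 = 35.

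**Events under the rule as written.** Every participant falls into one of two classes:

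| Participant | Code under 6.5.6 | Event? |
|---|---|---|
| Discontinues | 1 (censored at that date) | No |
| Does not discontinue | cannot be 0, since the event never occurs | No |

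The estimator is CIF(t) = 1 − ∏(1 − dᵢ/nᵢ), where dᵢ is the number of events and nᵢ the number at risk at each time. With every dᵢ = 0, the product is 1 and CIF(t) = 0 at all times. This holds for 2 plots × 8 groups = 16 curves and does not depend on the discontinuation rate.

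**Events with discontinuation coded 0.** Take the study-discontinuation plot over all participants, with completers censored only after the last drop-out. The product then reduces to the fraction completing.

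| Assumed discontinuers of 140 | Source | Events, as written | CIF, as written | Events, corrected | Final CIF, corrected |
|---|---|---|---|---|---|
| 35 | planned 25% | 0 | 0.0% | 35 | 1 − 105/140 = 25.0% |
| 9 | 6/98 = 6.12%; 140 × 0.0612 = 8.6 | 0 | 0.0% | 9 | 1 − 131/140 = 6.4% |

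Running the Appendix 2 coding on 140 participants gave the same values. The second row is a low-end illustration, because the earlier study dosed for only 28 days. The 25% is stated for the whole study population, so it is not split by arm. It is not applied to the IP plot either, because Protocol 7.1 separates stopping IP from leaving the study and no IP-discontinuation rate is given.

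**Comparison with the other plots.** In SAP 6.1.1.2.6, participants who discontinue or start glycemic rescue "prior to the start of the TEAE of interest will be censored at the discontinuation/initiation date". That works because the event there is an adverse event, distinct from the reason for censoring. SAP 6.1.1.2.7 concerns IP discontinuation due to gastrointestinal AEs. It also censors discontinuers without qualification, but it can sensibly be read as censoring those who stop for other reasons. SAP 6.5.6 covers discontinuation for any reason, so no such remaining group exists.

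**The case against.** The strongest reply is that nobody will be misled. SAP 6.5.6 names discontinuation as the event, SAP 5.2.4 plots time to the event, and Appendix 2 codes the event as 0. Only the last sentence of 6.5.6 conflicts. Flat curves would also contradict the discontinuation counts required by SAP 6.5.2 and should be caught at the first review of outputs. The plots are exploratory, and 5.2.4 says: "No statistical testing for differences between treatment groups will be considered". The point is then close to editorial. This stands as a limit on severity. It does not remove the error, because 5.2.4 sends the reader to 6.5.6 for censoring and no other passage corrects the rule.

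A second reply is that the sentence means cross-censoring, with study withdrawal censoring the IP curve and the reverse. The wording does not support this. The rule applies to both plots and ties each to its own associated date, and the IP plot is meant to disregard study status. Protocol 7.2 also treats withdrawal from the study as permanent discontinuation of IP, so withdrawal during treatment is itself an IP discontinuation.

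A third reply is that SAP 6.1.1.2.7, read just as strictly, would lose its events too. That is fair: its wording is similar and would benefit from a qualifier. The difference is that it has a coherent reading and 6.5.6 has none.

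Finally, the drop-out arithmetic only illustrates size. That is also true; the zero follows from the coding alone.

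**Conclusion.** The concern holds, as a minor error. Under the stated rule both discontinuation plots have zero events, and all 16 curves stay at 0%. That result rests only on the wording of SAP 6.5.6, SAP 5.2.4 and Appendix 2. The comparison for the study-discontinuation plot does rest on an assumption: about 35 of 140 (25.0%) at the planned drop-out rate, or about 9 of 140 (6.4%) at the earlier study's rate. No comparison is claimed for the IP plot.

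Only the timing display is affected. Disposition counts (SAP 6.5.2), the AE-discontinuation tables (SAP 6.5.6) and every primary and secondary analysis are unchanged. The absence of an explicit rule for completers is not counted as a defect in itself, since SAP 6.1.1.2.6 has none either.

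**What to change.** Replace the last sentence of SAP 6.5.6 with:

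> Discontinuation from the study (or IP) is the event (censor = 0). Participants who complete the study (or 12 weeks of IP) are censored (censor = 1) at their last study visit or contact (or last dose of IP).

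Both completion terms are already in the documents: the study through Visit 11 (Protocol 4.4) and IP by 12 weeks of treatment (SAP 3.5.1.2). The words *or contact* are included because the schedule of activities allows Visit 11 to be a telephone contact.

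Optionally, clarify SAP 6.1.1.2.7:

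> Only IP discontinuations due to Gastrointestinal Disorders AEs are events; participants who stop IP for other reasons are censored at that date.

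The cost is one SAP sentence, or two with the option. No new data are needed, and SAP 5.2.4 and Appendix 2 stay as they are.

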### **6.6. Safety Summaries and Analyses**

#### **6.6.1. Adverse Events**

Described in Section 6.1.1.

## 6.6.2. Laboratory Data

Laboratory data from will be listed and summarized by treatment group and overall, in accordance with the sponsor reporting standards.

Baseline is as defined in Section 3.

### 6.6.2.1. Focused Laboratory Summaries on Endpoints of Interest

Absolute values, changes from baseline and percent changes from baseline in calcitonin, amylase, lipase, TSH, free T4, lipid profile, liver function tests (i.e. ALT, AST, alkaline phosphatase, total bilirubin, bile acids and GGT) and eGFR (as outlined in Section 3.5.3.1) will be summarized by treatment and time point as per Section 5.2.1 (unplanned readings will not be included in these summaries). Follow-up data will be included in the summaries with data from all participants in the safety analysis set. Tables will be paged by parameter. Baseline is as defined in Section 3.

The following box and whisker plots for each parameter will be produced:

- Absolute values over time by treatment
- Change from baseline over time by treatment
- Percentage change from baseline over time by treatment

MMRM models (as described in Section 5.2.3) will be applied to the change from baseline at Weeks 2, 4, 6, 8, 10 and 12 (as applicable) for each parameter (except triglycerides, ALT, AST, Alkaline Phosphatase and GGT) and population (T2DM or non-diabetic participants with obesity) separately using the safety analysis set (as defined in Section 4). From each model, the LSMeans together with 90% confidence intervals, standard errors and p-values will be obtained for each treatment group at each time point. Differences in LSMeans between each treatment group of PF-06882961 relative to placebo (from the same population as restricted within the model) at each time point, together with 90% confidence intervals, standard errors and 2-sided p-values will also be obtained. A plot of the LSMean differences to Placebo (including 90% confidence intervals) over time, with a separate line for each treatment group of PF-06882961 will be produced separately for each parameter and population. Standard SAS outputs will be provided to support the main statistical summary tables but will not be included in the CSR.

Additionally, MMRM models will be applied to the percent changes from baseline in Triglycerides, ALT, AST, Alkaline Phosphatase and GGT for each parameter and population (T2DM or non-diabetic participants with obesity) separately. Similar to 6.2.3.2, the loge changes from baseline will be modelled and results will be back-transformed for reporting. Similar outputs to the absolute change from baseline MMRM models described above will be generated (including plots of LSMean differences to placebo).

After review of unblinded tables, if MMRM diagnostics reveal that any residuals deviate substantially from a normal distribution that, for example, require log transformation, the

MMRM model will be updated as necessary (e.g. apply log transformation and report modelled percent change from baseline).

